2.4.1. Exploratory Endpoints

- The number of subjects in each vaccine group with postoperative ISA disease occurring within 90 days of elective open posterior spinal fusion procedures with multilevel instrumentation.
- The number of subjects in each vaccine group with postoperative ISA disease occurring within 180 days of elective open posterior spinal fusion procedures with multilevel instrumentation.
- The number of subjects in each vaccine group with postoperative *S aureus* BSI and/or deep incisional or organ/space SSI occurring within 90 days of elective open posterior spinal fusion procedures with multilevel instrumentation, based on baseline *S aureus* colonization status.
- The number of subjects in each vaccine group with postoperative *S aureus* BSI and/or deep incisional or organ/space SSI occurring within 180 days of elective open posterior spinal fusion procedures with multilevel instrumentation, based on baseline *S aureus* colonization status.
- The proportion of subjects at each time point who achieve specific antibody thresholds in antibody assays that assess functional activity. These may include, for example, opsonophagocytic activity (OPA) assays using an *S aureus* capsular polysaccharide serotype 5 (CP5)-expressing strain and a capsular polysaccharide serotype 8 (CP8)-expressing strain, and competitive Luminex immunoassays (cLIAs) for ClfA and MntC. Additional exploratory assays to measure immune responses may also be conducted on all 4 antigens.
- The proportion of subjects at each time point who achieve specific antibody thresholds to all 4 antigens both individually and combined using immunological assays.
- The number of subjects in each vaccine group determined to be colonized with *S aureus* on each occasion swab samples are collected.

- From subjects with *S aureus* infection, the association between *S aureus* strain or strains identified as colonizing the subject and the *S aureus* strain or strains recovered from the infection.
- Healthcare utilization data, including days in hospital, days in an ICU, discharge disposition, inpatient days in rehabilitation facilities or skilled nursing facility after discharge, number of hospital readmissions and reoperations, days of antibiotic use, and number of rehabilitation/physical therapy outpatient visits.

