5.4. Concomitant Medication(s), Vaccinations, and Blood Products

The following concomitant medications, vaccinations, and blood products will be recorded in the CRF:

- Antibiotics, including all antibiotic use from study enrollment until completion of study participation, start and stop dates, name of antibiotic, dose, route, and frequency.
- Systemic steroids, from study enrollment until completion of study participation, start and stop dates, medication name, dose, units, route, frequency, and indication for use.
- Intraspinal steroids, from 6 months prior to study enrollment until completion of study participation, including medication name and date administered.
- Nonstudy vaccines administered from 6 months prior to study enrollment until completion of study participation, including name of vaccine and date administered.
- Blood products, including number of units and type (eg, whole blood, red blood cells, platelets, clotting factors, cryoprecipitate, white blood cells, immunoglobulins, albumin, and plasma). In addition, whole blood and red blood cells should be identified as heterologous or autologous donations. If a cell saver is used to return the subject's red blood cells during the index surgical procedure, this information will be recorded. All blood product use should be recorded from study vaccination through study completion.

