Appendix 3. Perioperative Assessment

- Skin preparation (eg, betadine, chlorhexidine)
- Surgical procedure performed (eg, posterior lumbar interbody fusion)
- Wound classification (eg, clean, clean contaminated, contaminated)
- Skin closure type (eg, staples, sutures, other)
- Primary incision site (eg, midline posterior, posterolateral)
- Secondary incision(s)
 - Spinal site(s) (anterior, endoscopic, etc.)
 - Graft donor site(s)
- Intervertebral level(s) fused (eg, lumbar 4 through thoracic 5)
- Implanted material (type and composition eg, rod, titanium)

- | Device Type | Composition |
|--------------------|--------------------|
| • Rods | • Titanium |
| • Plates | • Stainless steel |
| • Screws | • Other |
| • Cages | |
| • Other | |
- Graft type (eg, autograft, allograft, bone morphogenic protein, other)
 - Duration of surgery (knife to skin closure)
 - Surgical site drains, indwelling catheters

- Vancomycin powder application to wound
- Prophylactic antibiotic (name, start and stop time, date, and dose)
- Estimated blood loss (mL)
- Blood product transfusion (eg, whole blood, red blood cells, platelets, clotting factors, cryoprecipitate, white blood cells, immunoglobulins, albumin, and plasma) and origin (heterologous or autologous donation/ transfusion of whole blood or red blood cells)
- Postoperative patient temperature (°C or °F) (first recorded postoperative value on return to ward)

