#### **8.1.2.4. Concomitant Medications, Vaccinations, and Blood Products**

Antibiotics and systemic steroids will be summarized over 3 intervals:

1. The day of vaccination until the day before surgery, inclusive
2. The day of surgery until study completion (or dropout or withdrawal), inclusive
3. The day of vaccination until study completion (or dropout or withdrawal), inclusive

Intraspinal steroids will be summarized over 2 intervals:

1. 6 Months before study enrollment until the day before vaccination
2. The day of vaccination until completion of study participation

Nonstudy vaccines will be summarized over 2 intervals:

1. 6 Months before study enrollment until the day before vaccination
2. The day of vaccination until completion of study participation

Subjects will be counted once for each product in each interval. A subject will be included in the specified interval if either the start date or the stop date is contained in the interval.

Antibiotics, systemic steroids, intraspinal steroids, and nonstudy vaccines will be compared using the Fisher exact test, 2-sided.

Days of antibiotic use will be summarized over the same 3 intervals as antibiotics and systemic steroids. Any antibiotic uses that start before surgery and end after surgery will be split into 2 segments: the start of use until the day before surgery and the day of surgery to the end of use. The statistical test will be van Elteren, with site as a classification variable.

Use of blood products will be summarized over 3 intervals:

1. The day of vaccination until before surgery
2. Days 1-7 (where Day 1 is the day of surgery)
3. Days 8 or more

Use of blood products will be summarized as follows in each interval:

- Numbers and proportions of subjects receiving at least 1 transfusion will be compiled by vaccine group. The denominator will be the number of subjects in the time interval, ie, whose date of completion, dropout, or withdrawal is on or after the last day of the interval. The statistical test will be the Cochran-Mantel-Haenszel (CMH) test.
- The number of units will be summarized by n, mean, standard deviation, minimum, and maximum. Units will be obtained as the sum of all units received in the indicated interval. Vaccine groups will be compared using the van Elteren test, 2-sided. Only subjects receiving at least 1 transfusion will be included.

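### Optional improvement: the postoperative antibiotic comparisons in SAP 8.1.2.4 count surgical prophylaxis, which leaves the any-use test almost unable to show a difference in treatment courses

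*SAP*

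**What the plan says.** Protocol 2.4.1 lists "days of antibiotic use" among the healthcare-utilization data that form an exploratory endpoint. Protocol 5.4 has the CRF record "Antibiotics, including all antibiotic use from study enrollment until completion of study participation". For systemic steroids that section also asks for the indication; for antibiotics it does not.

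SAP 8.1.2.4 sets three intervals for antibiotics. The first ends the day before surgery. The second is "The day of surgery until study completion (or dropout or withdrawal), inclusive". The third runs from vaccination to study completion and so also contains the day of surgery. For use, "Antibiotics, systemic steroids, intraspinal steroids, and nonstudy vaccines will be compared using the Fisher exact test, 2-sided", with the counting rule "Subjects will be counted once for each product in each interval". For days, the SAP states "Days of antibiotic use will be summarized over the same 3 intervals as antibiotics and systemic steroids" and then "The statistical test will be van Elteren, with site as a classification variable". A course that spans surgery is split, and the part from the day of surgery onward goes to the postoperative segment. Table 21 repeats this plan in the safety population.

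Prophylaxis is captured separately. Protocol Appendix 3 lists "Prophylactic antibiotic (name, start and stop time, date, and dose", and SAP 6.3.2 tabulates prophylaxis given shortly before incision or repeated during surgery. Neither SAP 8.1.2.4 nor Table 21 refers to that record. SAP 6.3.3 and Table 24, which cover healthcare utilization, do not include antibiotic days.

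**The concern.** A vaccine that prevents infection would change treatment courses, not prophylaxis given around the incision. Protocol 1.2.2 names preoperative prophylactic antibiotics among the existing preventive measures, so many subjects in both arms will be antibiotic users on Day 1 whatever happens later. Someone who received prophylaxis and is later treated for infection is then the same any-use count as someone who received prophylaxis alone.

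The risk is a misleading null result. The tests are two-sided and sit among the safety methods, so the dilution could hide an increase in treatment antibiotics as easily as a decrease. A nonsignificant result could be read as no difference in antibiotic use when the comparison had little chance of showing one.

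**Working it through.** **Inputs.** Protocol 9.2 gives a placebo incidence of about 1.4%, VE of 70% and dropout of 10%. The SA4Ag rate is 0.014 × (1 − 0.70) = 0.0042. About 6000 enrolled at 1:1 gives 3000 per arm, and 3000 × 0.90 = 2700. Not given in the documents and therefore assumed: prophylaxis coverage q, the share b of subjects given antibiotics for other reasons, course lengths, and a two-sided alpha of 0.05.

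**The plan's own figures.** Enrollment = 48 / (mean case rate) / 0.90.
- VE 70%: mean rate (0.014 + 0.0042)/2 = 0.0091, giving 5861 (plan: about 6000).
- VE 60%: mean rate (0.014 + 0.0056)/2 = 0.0098, giving 5442 (plan: about 5440).
- The binomial probability of 14 or fewer of 48 at 0.230 is 0.880 (plan: 0.88).

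The planning rates are therefore sound inputs. The documents state no power for the antibiotic comparison itself.

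**Any use.** The user proportion is 1 − (1 − q)(1 − b)(1 − case rate), so the difference between arms is (1 − q)(1 − b) × 0.0098. At q = 98% and b = 0 the arms are 98.03% and 98.01%: a gap of 0.98 points becomes 0.02 points. Power is approximated by Φ(|p₁ − p₂|/SE − 1.96), with SE = √{[p₁(1 − p₁) + p₂(1 − p₂)]/2700}. Two examples at b = 0:
- q = 0: SE = 0.00258, 0.0098/0.00258 = 3.80, power Φ(1.84) = 97%.
- q = 25%: proportions 0.2605 and 0.2531, SE = 0.0119, 0.00735/0.0119 = 0.62, power Φ(−1.34) = 9%.

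| Prophylaxis coverage | b = 0 | b = 5% | b = 10% |
|---|---|---|---|
| none counted | 97% | 31% | 18% |
| 25% | 9.0% | 8.1% | 7.4% |
| 50% | 5.5% | 5.3% | 5.1% |
| 80% | 3.8% | 3.7% | 3.7% |
| 98% | 2.8% | 2.8% | 2.8% |

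The formula counts rejections in one direction only, so 2.5% means no information.

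**Days, unstratified rank test.** Simulated with the same rates, 2700 per arm, 3000 replicates. Assumed treatment lengths are 14–56 days for cases and 3–14 days for other use.

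| Prophylaxis | b = 0 | b = 5% | b = 10% |
|---|---|---|---|
| removed | 97% | 32% | 22% |
| 100% coverage, all 1 day | 98% | 35% | 20% |
| 98% coverage, all 1 day | 58% | 26% | 20% |
| 98% coverage, 1 day, one course in five 2 days | 15% | 13% | 12% |
| 98% coverage, 1–3 days at random | 10% | 11% | 10% |

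A uniform course shifts every rank equally and costs nothing beyond simulation error. The loss comes from variation among subjects who have no treatment course.

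**Days, site-stratified test as planned.** The van Elteren test ranks within site, so only variation within site matters. A simulation with 3000 per arm shows the range. It assumed prophylaxis of 1–3 days and, for illustration only, treatment courses of 5–42 days in 10% vs 13% of subjects. Power was 96% with no prophylaxis, 96% if length is set by site, 84% if it is mostly set by site, and 56% if it is random within site. The documents do not say which pattern applies.

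**The case against.** The strongest reply is that the SAP analyses what the protocol defines. The endpoint is total days of antibiotic use, with no restriction to treatment, and total use is a legitimate measure of exposure and resources. That stands, and it is why the all-inclusive summary should remain. It does not make the any-use test informative about treatment.

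Three stronger readings are tempting, and the documents do not support them.
- A reader might infer that the days test also loses most of its power. The planned test is stratified by site, and if sites apply their own standard course nothing is lost.
- A reader might infer that SAP 8.1.2.4 holds the only planned analysis of antibiotic days. It holds the only explicit one in the SAP, but protocol 9.4.2 also plans descriptive statistics and 95% CIs for the mean or median difference. Prophylaxis that is balanced by randomization does not bias a mean difference.
- A reader might infer that removing prophylaxis would rescue the comparison. With 5–10% other antibiotic use, power is only 18–32% even then.

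Two further limits stand. If each product means each drug, saturation falls mainly on the prophylactic drugs. And SAP 8.1.3.5 records that the study met futility and ceased enrollment in December 2018. The figures here use the planned size, and no decision on efficacy turns on this table, because infection is tested directly in the primary and secondary endpoints.

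**Conclusion.** The point holds as an optional improvement, not as a defect that must be corrected. Prophylaxis on the day of surgery is counted in the postoperative and whole-study intervals. With the protocol's rates, any-use power is then below 10% at coverage of 25% or more, against 97%, 31% or 18% without prophylaxis at 0%, 5% or 10% other use. This does not depend on near-universal prophylaxis, a rate the documents do not state. It does assume that use is tabulated for antibiotics as a class, and that the effect is limited to primary endpoint cases; superficial SSI would add to the effect. For days, the loss lies between none and large, according to within-site variation that the documents do not give, so no single figure should be quoted.

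**What to change.** In SAP 8.1.2.4 and Table 21, keep the all-inclusive summary of use and days as descriptive. For the postoperative and whole-study intervals, add the Fisher and van Elteren comparisons for non-prophylactic antibiotics. Identify prophylaxis by matching the concomitant-medication record to the Appendix 3 record on drug, start and stop, and count any days after the recorded prophylaxis stop as use.

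A shortcut that counts only courses starting after Day 2 should not be used. It drops treatment begun on Days 1–2, although SAP 6.1 counts endpoint onset from Day 1, and it drops whole courses that begin as prophylaxis and continue as treatment.

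The cost is SAP wording and one derivation from data already collected. The match is approximate, because protocol 5.4 lists no indication for antibiotics. The comparison remains exploratory and unpowered, and the table should say so.

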Organ failure events	Organ failure events from after surgery to Day 180 (applicable during any hospitalization)							

Abbreviations: AE = adverse event; N/A = not applicable; PDI = protocol-defined infection; SAE = serious adverse event.

a. If surgery occurs on Day 10 after vaccination, the e-diary need not be completed on the day of surgery.

UNSCHEDULED STUDY VISITS, CONTACTS, AND SURVEILLANCE PERIODS

Table 3 shows the list of unscheduled visits that are to occur when certain conditions are met. Refer to Table 4 for unscheduled visit procedures.

Table 3. Unscheduled Study Visits, Contacts, and Surveillance Periods

Visit ID	1	2			3	4	5	6
Protocol Activity	Enrollment and Day of Vaccination	Index Hospital Admission			Telephone Call 	Day 42 Postoperative Evaluation	Day 90 Postoperative Evaluation	Day 180 Postoperative Evaluation
		Day of Surgery	Day After Surgery	Day of Discharge				
Study Day	Day -60 to Day -10	Day 1	Day 2	(Day Variable)	Day 21	Day 42	Day 90	Day 180
Visit Window	Day -60 to Day -10	N/A	N/A	N/A	Day 18 to Day 26	Day 35 to Day 49	Day 83 to Day 97	Day 178 to Day 192
UNSCHEDULED VISITS AND CONTACTS								
Severe local reaction or fever telephone contact  (Section 6.4.1.1.1)	May occur within 10 days after vaccination							
Severe systemic event telephone contact  (Section 6.4.1.1.2)	May occur within 10 days after vaccination							
Severe local reaction or fever assessment visit (Section 6.4.1.2)	May occur within 10 days after vaccination							
BSI/SSI assessment visit (Section 6.4.2)		
 • May occur postoperatively during the index hospital admission • May occur after discharge from the index hospital 						
Hospitalization visit (Section 6.4.3)		May occur at any time after discharge from the index hospital						

Abbreviations: BSI = bloodstream infection; N/A = not applicable; SSI = surgical-site infection.

STUDY PROCEDURES ASSOCIATED WITH UNSCHEDULED STUDY VISITS

The Study Procedures Associated With Unscheduled Study Visits table provides an overview of the unscheduled visit requirements. Refer to the Study Procedures ([Section 6.4](#)) and Assessments ([Section 7](#)) sections of the protocol for detailed information on each procedure and assessment required for compliance with the protocol.

Table 4. Study Procedures Associated With Unscheduled Study Visits

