### **8.1.2. Methodology for Safety Endpoints**

The denominators for all proportions will be the number of subjects in the vaccine group, except where noted.

All CIs for proportions will be 2-sided 95% intervals, obtained using the Clopper-Pearson method. There will be no adjustments for multiplicity.

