- Counts of transfusions per subjects (values 0, 1, 2, etc) will be compiled by vaccine group. Vaccine groups will be compared using the van Elteren test, 2-sided.
- Counts of transfusions will be further split by types of transfusions, also compiled by vaccine group. The types of transfusions will be packed RBCs, platelets, whole blood, plasma, and other. The denominator will be the number of subjects in the time interval. The statistical test will be the CMH test, 2-sided.
- Numbers and proportions of subjects receiving heterologous donation or autologous transfusions will be compiled by vaccine group. The denominator will be the number of subjects receiving packed RBCs or whole blood. The statistical test will be the CMH test, 2-sided.
- Numbers and proportions of subjects using cell saver will be compiled by vaccine group. The statistical test will be the Fisher exact test, 2-sided. Only subjects receiving at least 1 transfusion will be included.

All CMH tests will use site as a stratification factor.

Subjects who have more than 1 transfusion in the specified interval will not be counted more than once for any given category (eg, platelets), but will be counted for each separate category (eg, platelets for one transfusion and whole blood for a different transfusion).

Statistical analyses are summarized in [Section 8.2.2.4](#).

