**Table 21. Summary of Analyses for Concomitant Medications, Nonstudy Vaccines, and Blood Products**

Endpoint	Population	Statistical Method	Model/Covariates/Strata	Missing Data	Interpretation/Comments
Days of antibiotic use	Safety	van Elteren	Vaccine group; site for van Elteren test	N/A	3 Time intervals: 1. The day of vaccination to the day before surgery 2. The day of surgery until study completion 3. The day of vaccination until study completion
Blood products: transfusions (blood product type, origin of blood product if packed RBCs or whole blood, use of cell saver, number of units, number of transfusions per subjects)	Safety	CMH for discrete variables, van Elteren for number of units and number of transfusions	Vaccine group; site for van Elteren test	N/A	3 Time intervals: 1. The day of vaccination until before surgery 2. Days 1-7 (where Day 1 is the day of surgery) 3. Days 8 or more

Abbreviations: CMH = Cochran-Mantel-Haenszel; N/A = not applicable; RBC = red blood cell.

All analyses will be conducted in the safety population. No subgroup analyses are proposed.

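### Transfusion proportions count only subjects who reach the end of the interval, and the interval from Day 8 onwards has no stated end

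*SAP*

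**What the plan says.** SAP Section 8.1.2.4 summarizes blood products over three intervals: vaccination until before surgery, Days 1-7 counted from surgery, and Day 8 onwards. For the proportion with at least 1 transfusion, the denominator is limited to subjects "whose date of completion, dropout, or withdrawal is on or after the last day of the interval". The summary by type of transfusion uses the same set: "The denominator will be the number of subjects in the time interval". Both are tested by Cochran-Mantel-Haenszel (CMH), and "All CMH tests will use site as a stratification factor".

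This departs from the general safety rule in SAP Section 8.1.2: "The denominators for all proportions will be the number of subjects in the vaccine group, except where noted".

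The third interval appears in SAP Table 21 only as "3. Days 8 or more". Neither the table nor Section 8.1.2.4 gives it a last day. The antibiotic and systemic steroid intervals in the same section do name their end, at study completion, dropout or withdrawal.

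Protocol Section 5.4 sets the collection period: "All blood product use should be recorded from study vaccination through study completion". The final visit may fall anywhere in "Day 178 to Day 192" (Protocol Table 3). The SAP states no matching restriction on the numerator.

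**The concern.** A transfusion can be observed from the first day of an interval, but membership of the denominator is decided by being present on its last day. A subject transfused on Day 1 who leaves on Day 5 has a recorded transfusion and is not in the Days 1-7 denominator. The rule does not mention death, but by inference an early death is excluded too: either it is coded as a dropout or withdrawal before Day 7, or the subject has no qualifying date.

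The third interval raises a different problem. The rule refers to a last day that the plan never gives, so two programmers could build different denominators, and different CMH tables, from the same text. Because the numerator is not tied to the same subjects, one possible result is a proportion in which transfused subjects are counted above the line and missing below it.

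**Working it through.** The plan states no transfusion rate and no expected figure for this analysis, so there is nothing of its own to reproduce. The check applies the written rule to each interval.

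**Inputs from the documents.** About 6000 subjects (Protocol Section 3.1), allocated 1:1 (Section 3), so about 3000 per arm. Total dropout 10% (Section 9.2, where it is an enrollment-planning assumption). Final visit Days 178-192, which is 15 days.

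**Assumptions, not in the documents.** The number of early leavers, the transfusion rates, the timing of dropout, and the spread of final visits.

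**Days 1-7.** Suppose 20% of stayers and 90% of early leavers are transfused. With 30 leavers among 3000:

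- All subjects at risk: (2970 × 0.20 + 30 × 0.90) / 3000 = 621/3000 = 20.70%.
- SAP rule, numerator restricted: 594/2970 = 20.00%.
- SAP rule, numerator unrestricted: 621/2970 = 20.91%.

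With 15 leavers the three results are 20.35%, 20.00% and 20.45%. With 3 leavers they are 20.07%, 20.00% and 20.09%. Every difference from the at-risk figure is under 1 percentage point.

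**Day 8 onwards, subject's own last day.** Every subject meets the rule, including those gone before Day 8, so the denominator is the whole arm. If all of the 10% dropout came before Day 8, the at-risk set would be 0.90 of the arm, and this reading would understate the proportion by a factor of 0.90/1.00, or 10%. If nobody left before Day 8, it would be exact.

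**Day 8 onwards, last day = Day 180.** Let *e* be the share of completers whose final visit was on Day 178 or 179, and *b* the share of dropout that occurs before Day 8.

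- Denominator under the rule: (1 − 0.10)(1 − *e*). With visits uniform over 15 days, *e* = 2/15 and the denominator is 0.90 × 13/15 = 0.78.
- Subjects at risk on Day 8: 1 − 0.10*b*, which is 1.00, 0.95 or 0.90 for *b* = 0, 0.5 or 1.
- If the numerator is unrestricted, the inflation factor is the second divided by the first:

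| *e* | Denominator | *b* = 0 | *b* = 0.5 | *b* = 1 |
|---|---|---|---|---|
| 0 | 0.900 | 1.11 | 1.06 | 1.00 |
| 0.05 | 0.855 | 1.17 | 1.11 | 1.05 |
| 2/15 (uniform) | 0.780 | 1.28 | 1.22 | 1.15 |
| 0.15 | 0.765 | 1.31 | 1.24 | 1.18 |

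For example, take 150 transfused subjects in an arm of 3000 with uniform visits. The Day 180 denominator is 0.78 × 3000 = 2340 and the proportion is 150/2340 = 6.41%. The at-risk figure is 150/3000 = 5.00% if *b* = 0 and 150/2700 = 5.56% if *b* = 1.

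If the numerator is restricted to the same 2340 subjects, none of these factors applies. What remains is selection of the subjects who stayed to Day 180.

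**The case against.** The best defense is that the plan can be read sensibly. A CMH table needs its transfused subjects to be a subset of its denominator, so the planned test itself points to a restricted numerator, and then the inflation disappears. The neighboring antibiotic and steroid intervals end at completion, dropout or withdrawal. If the third blood-product interval is closed in the same way, no later dropout or completer is lost. Removing completers because they were seen on Day 178 or 179 has no evident link to transfusion. Other summaries in the same section (units among transfused subjects, and counts of transfusions per subject) carry no stated end-of-interval restriction, so early leavers' transfusions can still appear there. The heterologous or autologous and cell-saver proportions have their own bases. Transfusion is not among the protocol's primary safety endpoints.

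All of this stands, and it limits the size of the point. It does not restore early leavers to Days 1-7, and it does not supply the missing last day. The sensible reading has to be chosen by the programmer because the SAP does not choose it.

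A reader might go further and infer that the third interval has no usable denominator, or that only 0.90 × 1/15 = 6% of subjects would remain if the last day were Day 192. The documents do not support either. The denominator is unspecified, not unobtainable, and nothing suggests that Day 192 was meant.

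**Conclusion.** The point holds as a minor flaw in a supportive safety summary. As written, the rule conditions on staying to the end of the interval, and for Day 8 onwards it leaves that end open. For Days 1-7 the effect is probably under 1 percentage point, on the assumed leaver counts and transfusion rates. For Day 8 onwards the size depends on two choices the SAP leaves open. Under the Day 180 reading with an unrestricted numerator, the proportion is inflated by about 15% (all dropout before Day 8) to 28% (none before Day 8) in relative terms, given 10% total dropout and uniform final visits. The upper figure should not be quoted alone, because it needs every dropout to occur after Day 7. With a restricted numerator there is no such inflation.

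It is also tempting to infer that the rule removes the sickest subjects and so distorts the comparison of SA4Ag with placebo. The rule is the same in both arms, and the documents give no transfusion or early-exit figures by arm, nor any for early leavers. No between-arm bias is shown, and no efficacy conclusion is touched.

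**What to change.** In SAP Section 8.1.2.4, define the denominator as subjects in the study on the first day of each interval:

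- vaccination until surgery: all vaccinated subjects;
- Days 1-7: all subjects who had surgery;
- Day 8 onwards: subjects still in the study on Day 8.

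State that the numerator and the CMH test use the same set. End the third interval at each subject's completion, dropout, withdrawal or death, and repeat that end point in Table 21. The change costs a sentence or two in the SAP and a revised denominator flag in programming. No data collection changes.
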